5.5.2. Analysis Methods

All exploratory endpoints will be analyzed using the FAS. The analysis may be repeated in the IFN-FAS and modified FAS/IFN-FAS analysis sets if there is a difference of at least 2 participants between analysis sets.

Some analysis will be performed by group, as defined in Section [5.1.10](#).

Summaries and graphs will be provided for each analysis phase, unless specified otherwise.

All exploratory endpoints will be analyzed based on the observed case data. No imputation for missing data will be used.

5.5.2.1. Binary Endpoints

The methods of analysis of the binary exploratory endpoints will be the same as those described in Section [5.4.2.1](#).

5.5.2.1.1. Liver Stiffness Measurement

The count and proportion of participants who meet those change from baseline thresholds for LSM during the study will be summarized at Week 24, FU Week 24 and FU Week 48.

At each assessment time point, a frequency distribution of severity scores will be produced.

5.5.2.1.2. HBV RNA Cut-offs

The cut-offs for HBV RNA values, decreases from baseline, and RT will be used in separate summaries over time. The number and proportion of participants who meet those HBV RNA thresholds during the study will be summarized descriptively by analysis phase over time and displayed in graphs like bar charts.

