In currently not treated HBeAg-positive participants (mean baseline HBV DNA levels 7.65 to 8.24 \log_{10} IU/mL), there were pronounced declines in mean (standard error [SE]) HBV DNA from baseline of 5.53 (0.23) and 5.88 (0.34) \log_{10} IU/mL for JNJ-6379 75 mg and 250 mg + NA, respectively, and 5.21 (0.42) \log_{10} IU/mL for placebo + NA. In currently not treated HBeAg-negative participants (mean baseline HBV DNA levels 4.89 to 5.40 \log_{10} IU/mL), interpretation of mean (SE) HBV DNA decline was confounded since many participants had HBV DNA < lower limit of quantification (LLOQ) from Week 4 onwards.

In currently not treated participants, JNJ-6379 75 mg and 250 mg + NA showed a clear mean (SE) HBV RNA decline from baseline (2.82 [0.25] and 3.13 [0.35] \log_{10} copies/mL, respectively) compared with placebo + NA (1.43 [0.32] \log_{10} copies/mL), thereby differentiating JNJ-6379 from

NAs. HBV RNA was target not detected (TND) at Week 24 in 16/27 (59%), 19/25 (76%) and 9/20 (45%) participants, respectively.

The 24-week interim efficacy data in virologically suppressed participants showed that most participants had HBV DNA levels below the limit of quantification at baseline. All virologically suppressed participants on JNJ-6379 + NA who had detectable HBV RNA at baseline achieved HBV RNA TND at Week 24 (13/13 participants on 75 mg JNJ-6379 and 8/8 participants on 250 mg JNJ-6379) vs 1/7 (14%) participants on placebo + NA.

In currently not treated HBeAg-positive participants, JNJ-6379 75 mg and 250 mg + NA resulted in a mean (SE) HBsAg decline of 0.13 (0.10) and 0.40 (0.15) \log_{10} IU/mL, respectively, compared with 0.22 (0.11) for placebo + NA at Week 24. Participants with HBsAg declines also had HBeAg declines and frequently had early on-treatment isolated ALT flares. In both JNJ-6379 + NA arms:

- Maximal individual HBsAg and HBeAg reductions were 1.28 and 1.8 \log_{10} IU/mL, respectively, at Week 24;
- The proportion of currently not treated HBeAg-positive participants with $>0.3 \log_{10}$ IU/mL reductions from baseline in:
 - HBsAg was 8/23 (35%) vs 1/8 (13%) for placebo + NA;
 - HBeAg was 19/23 (83%) vs 4/8 (50%) for placebo + NA;
- The proportion of virologically suppressed HBeAg-positive participants with $>0.3 \log_{10}$ IU/mL reductions in HBeAg was 7/19 (37%) vs 1/5 (20%) for placebo + NA.

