5.4.1.1.8. HBeAg Cut-offs

The cut-offs for HBeAg level are as follows:

- < 100 IU/mL
- < 10 IU/mL
- < 1 IU/mL
- < LLOQ (0.11 IU/mL)

Of note, seroclearance of HBeAg is defined as (quantitative) HBeAg <LLOQ.

The cut-offs for HBeAg change from baseline and RT are as follows:

- decrease by $\geq 0.3 \log_{10}$ IU/mL
- decrease by $\geq 0.5 \log_{10}$ IU/mL
- decrease by $\geq 1 \log_{10}$ IU/mL
- decrease by $\geq 2 \log_{10}$ IU/mL
- decrease by $\geq 3 \log_{10}$ IU/mL

Only HBeAg positive participants will be used for the analysis of the HBeAg cut-offs.

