5.5.1.1.2. HBV RNA Cut-offs

The cut-offs for HBV RNA are as follows:

- $< \text{LOD}$
- $< \text{LLOQ}$
- < 1000 copies/mL

The cut-offs for HBV RNA change from baseline and RT are as follows:

- decrease by ≥ 1.0 log copies/mL
- decrease by ≥ 2.0 log copies/mL
- decrease by ≥ 3.0 log copies/mL

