5.5.1.1.3. HBcrAg Cut-offs

The cut-offs for HBcrAg are as follows:

- < 3.0 log U/mL
- < 4.0 log U/mL

The cut-offs for HBcrAg change from baseline and RT are as follows:

- decrease by ≥ 1.0 log U/mL
- decrease by ≥ 2.0 log U/mL

- decrease by $\geq 3.0 \log U/mL$

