5.5.1.3. Time to Event Endpoints

5.5.1.3.1. Time to First HBV RNA<LOD

Time to first HBV RNA<LOD is defined as the duration from the date of first study intervention intake to the date of the first occurrence of HBV RNA<LOD (i.e. the date of the first occurrence of HBV RNA<LOD – the date of first study intervention intake + 1). The participants who did not achieve undetectability or who early withdrew from the study before achieving HBV RNA<LOD will be censored at the last HBV RNA assessment before the date of withdrawal.

Time to first HBV RNA<LOD will be also analyzed considering the participants who were retreated with NA before achieving HBV RNA<LOD as censored at the date of NA retreatment.

Only the participants with HBV RNA values $\geq LOD + 0.5 \log_{10} \text{ cp/mL}$ (i.e. $\geq 1.898 \log_{10} \text{ cp/mL}$) at baseline will be included in this analysis. Similarly, additional analyses for participants with HBV

RNA values $\geq \text{LOD} + 1.0 \log_{10}$ cp/mL and $\geq \text{LOD} + 2.0 \log_{10}$ cp/mL, respectively, will be summarized.

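### HBV RNA and HBcrAg cut-off and decline proportions set no condition on the starting level, so they count participants who cannot respond and participants who meet the cut-off before dosing

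*SAP*

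**What the plan says.** SAP 5.5.1.1.2 lists level cut-offs for HBV RNA (<LOD, <LLOQ, <1000 copies/mL). It then introduces decreases of at least 1, 2 and 3 log with "The cut-offs for HBV RNA change from baseline and RT are as follows". Section 5.5.1.1.3 lists <3.0 and <4.0 log U/mL for HBcrAg and introduces the same three decreases with "The cut-offs for HBcrAg change from baseline and RT are as follows". RT is the last value before the first PegIFN-α2a dose (SAP 5.1.5). None of these definitions mentions the starting level.

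Section 5.5.2.1.2 sets the HBV RNA analysis: "The number and proportion of participants who meet those HBV RNA thresholds during the study will be summarized descriptively by analysis phase over time". Section 5.5.2.1.3 does the same for HBcrAg. The population comes from SAP 5.5.2: "All exploratory endpoints will be analyzed using the FAS", and "All exploratory endpoints will be analyzed based on the observed case data. No imputation for missing data will be used". The denominator is therefore FAS participants with a result at the visit. It may be smaller still, because a footnote to the protocol's Schedule of Activities allows only selected HBV RNA and HBcrAg samples to be tested.

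SAP Table 5 sets HBV RNA below the LOD, or not detected, to 1.114 log10 cp/mL. It sets HBcrAg below 3.0 log10 U/mL to 2.7.

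**The concern.** The trial enrols only patients already suppressed on an NA (HBV DNA <60 IU/mL on two occasions, Protocol 5.1). Some will enter with these markers at or near the assay floor. They cannot show a decline, so they are certain non-responders in the decline tables. In the level tables they meet the lowest cut-off from Day 1. The decline rate then partly measures how many entered with room to fall, and the <LOD rate partly measures prior NA suppression.

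Elsewhere the SAP uses eligible denominators for this kind of problem:

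- Time to HBV RNA <LOD (5.5.1.3.1): only participants at or above LOD + 0.5 log10 "at baseline will be included in this analysis", with further sets at +1.0 and +2.0.
- Time to HBcrAg undetectability (5.5.1.3.2): baseline of at least 3.5 log10 U/mL.
- HBeAg cut-off proportions (5.4.1.1.8): "Only HBeAg positive participants will be used for the analysis of the HBeAg cut-offs".
- ALT normalization (5.4.2.1.12): only those with elevated ALT at baseline.

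The HBV RNA and HBcrAg proportions have no such denominator, although the protocol lists these markers under an exploratory efficacy objective.

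**Working it through.** **The plan's own figures.** log10(25) = 1.398 (LOD), log10(869) = 2.939 (LLOQ) and log10(13) = 1.114 (imputed floor) all match Table 5. The time-to-event thresholds reproduce: 1.398 + 0.5 = 1.898 and 3.0 + 0.5 = 3.5. The exact 90% interval for 25/50 reproduces as 0.376-0.624, as in SAP Table 1.

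**Starting level needed for a decline** = imputed floor + required fall.

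| Fall (log10) | HBV RNA, log10 cp/mL | HBcrAg, log10 U/mL |
|---|---|---|
| ≥1 | 1.114 + 1 = 2.114 (130 cp/mL) | 2.7 + 1 = 3.7 |
| ≥2 | 1.114 + 2 = 3.114 (1,300 cp/mL) | 2.7 + 2 = 4.7 |
| ≥3 | 1.114 + 3 = 4.114 (13,000 cp/mL) | 2.7 + 3 = 5.7 |

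Both time-to-event thresholds lie below the level needed for a 1-log fall (1.898 < 2.114; 3.5 < 3.7).

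**Share with detectable HBV RNA at entry, f.** The only figures are in Protocol 2.2.3.1, on the earlier Phase 2a study: "All virologically suppressed participants on JNJ-6379 + NA who had detectable HBV RNA at baseline achieved HBV RNA TND at Week 24" (13/13 and 8/8), against 1/7 on placebo + NA. That makes 13 + 8 + 7 = 28 detectable at baseline. The suppressed participants number 33 + 30 + 21 = 84, so f = 28/84 = 33% (exact 90% CI 25-43%).

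The protocol does not say that all 84 had a baseline RNA result, so two variations were tried:

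- *Smaller denominator.* In the untreated arms, Week 24 RNA status is given for 27 + 25 + 20 = 72 of 88 (82%). Then 84 × 0.818 ≈ 69, and f = 28/68.7 = 41%.
- *Re-weighting to 40% HBeAg-positive.* HBeAg data cover 19 + 5 = 24 HBeAg-positive suppressed participants. If all 24 had detectable RNA, f = 0.4 × 1 + 0.6 × 4/60 = 44%. If none did, f = 0.6 × 28/60 = 28%. With 69 in place of 84, the bounds are 0.4 + 0.6 × 4/45 = 45% and 0.6 × 28/45 = 37%.

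The range is 28-45%. Detectable participants would reach half only if the true denominator were 56.

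**Effect on the reported rates.** Let r be the response rate among those detectable at entry. The unrestricted <LOD rate is (1 − f) + f·r. The unrestricted decline rate is f·r and cannot exceed f.

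| | f = 33% | f = 28% to 45% |
|---|---|---|
| Day 1 <LOD, 1 − f | 67% | 72% to 55% |
| <LOD if r = 1/7 (the placebo + NA figure) | 0.667 + 0.333/7 = 71% | 76% to 61% |
| <LOD if r = 50% | 83% | 86% to 78% |
| Decline rate if r = 50% | 17% | 14% to 23% |
| Ceiling on decline rate | 33% | 28% to 45% |

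With N = 50, f = 33% gives about 17 detectable participants. Eight decline responders would be reported as 8/50 = 16% (90% CI 8.2-27.0), against 8/17 = 47% (26.0-68.9). The 8 is purely illustrative. The ceiling is itself generous, because participants between the LOD (25 cp/mL) and 130 cp/mL are detectable but cannot fall by 1 log.

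**HBcrAg.** Neither document gives a baseline distribution, so no rate can be computed.

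**The case against.** The strongest reply is that the plan already lets a reader see the floor. Table 4 makes baseline an analysis time point, so the Day 1 proportion below each level cut-off should appear in the over-time summary. Table 12 tabulates baseline HBV RNA and HBcrAg categories. The restricted Kaplan-Meier analyses give first achievement of <LOD, or of HBcrAg undetectability, among those who start above the floor. The protocol's stated endpoint is change over time, which SAP 5.5.2.2.2 covers with descriptive statistics, change to nadir and waterfall plots. No test is performed. The HBeAg restriction follows a protocol footnote that has no counterpart for these markers, so that parallel is imperfect. The unrestricted tables also have a use: in follow-up, when some participants stop NA, they show maintained undetectability and rebound in those undetectable at entry.

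Most of this stands, and it lowers the severity. It does not close the gap. Marginal baseline categories do not show how many of the eligible participants responded. The Kaplan-Meier analysis gives first occurrence, not status at a visit, and covers no decline. Table 8 has no subgroup by baseline HBV RNA or HBcrAg.

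Some stronger readings are tempting, and the documents do not support them:

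- *Most participants start at the floor for both markers.* There is no HBcrAg baseline information, and HBcrAg has no <LOD cut-off.
- *<LOD will in fact be largely met before dosing in this trial.* That is an inference from another study, whose assay limit and exact denominator are not given.
- *About 17 of 50 can respond.* Detectable is not the same as able to fall by 1 log.
- *Every FAS participant is in the denominator.* Only observed results are used.

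**Conclusion.** The point holds as a gap in the denominators. No planned table gives a by-visit rate below a level cut-off, or any decline rate, among participants who could achieve it. The attainability thresholds follow from Table 5 alone and need no assumption about this trial's population.

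The size for HBV RNA rests on carrying over 28/84 from the earlier study. On that assumption the decline rate is capped near one third (28-45%), and the Day 1 <LOD rate is near two thirds (55-72%). For HBcrAg only the structural point applies. The affected summaries are exploratory and descriptive, and they sit beside analyses that partly reveal the problem. Severity is low.

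**What to change.** Add the following to SAP 5.5.2.1.2 and 5.5.2.1.3, stating the denominator at every visit:

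- **Level cut-offs:** the proportion below each cut-off among participants at or above that cut-off at baseline.
- **Declines:** the proportion with each fall among participants whose starting value makes it attainable (HBV RNA at least 2.114, 3.114 or 4.114 log10 cp/mL; HBcrAg at least 3.7, 4.7 or 5.7 log10 U/mL). Use the baseline value for changes from baseline and the RT value for changes from RT. RT follows the JNJ-3989 + NA period, so a baseline condition does not settle who can still fall from RT.

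Do not reuse the 1.898 and 3.5 thresholds of 5.5.1.3.1 and 5.5.1.3.2 for the declines. They would keep some participants who cannot fall by 1 log.

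Keep the unrestricted FAS tables for maintained undetectability and rebound in follow-up.

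The cost is SAP wording and a denominator flag. The restricted sets will be small and their intervals wide: 10/20 gives a 90% CI of 0.302-0.698.

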5.5.2.1.3. HBcrAg Cut-offs

The cut-offs for HBcrAg values, decreases from baseline and RT will be used in separate summaries over time. The number and proportion of participants who meet those HBcrAg thresholds during the study will be summarized descriptively by analysis phase over time and displayed in graphs like bar charts.

5.5.2.1.4. Anti-HBe Antibodies

The number and proportion of participants with positive and negative anti-HBe values will be summarized descriptively by analysis phase over time.

Shift tables in Anti-HBe positive/negative values from baseline will also be provided at each time point.

5.5.2.2. Continuous Endpoints

The methods of analysis of the continuous exploratory endpoints will be the same as those described in Section 5.4.2.2.

5.5.2.2.1. Liver Stiffness Measurement

The changes from baseline at Week 24, FU Week 24, and FU Week 48 will be summarized using descriptive statistics (n, mean, SE, 90% CI, median, minimum, maximum).

Plots of mean (+/- SE) values and changes from baseline over time will be presented. In addition, a waterfall plot will be produced to display the individual changes from baseline in LSM for each participant at over time.

5.5.2.2.2. HBV RNA and HBcrAg

The actual values, changes from baseline and changes from RT in HBV RNA and HBcrAg, respectively, will be summarized only descriptively over time in a similar manner as for values, changes from baseline and changes from RT over time in HBsAg, HBeAg, and HBV DNA as described in Section 5.4.2.2.1, including the change from baseline value to nadir (i.e. maximum decrease for each participant) and the various graphical displays.

Waterfall plots for changes from baseline of HBV RNA and HBcrAg will also be presented over time.

5.5.2.2.3. Anti-HBs Antibodies

The actual values of and changes from baseline in anti-HBs antibodies will be summarized only descriptively in a similar manner as described for values and changes from baseline over time in other blood disease markers in Section 5.4.2.2.1.

For all participants with positive anti-HBs antibodies at baseline who will reach HBsAg seroclearance (as defined in Section 5.4.1.1.4), descriptive statistics will be calculated for the change of anti-HBs antibodies level from baseline at the timepoint when achieving the HBsAg seroclearance. In an additional summary, the change of anti-HBs antibodies level from baseline

at the specific timepoint will be summarized descriptively for the subset of the participants achieving HBsAg seroclearance at any time before or at that given timepoint if there is at least 10% of the participants for the subset.

5.5.2.3. Time to Event Endpoints

The time-to-event endpoints will be analyzed in a similar manner as for the time-to-event endpoints described in Section 5.4.2.3.

5.5.2.4. Endpoints for Correlation

5.5.2.4.1. Association Between Baseline Characteristics/Viral Blood Markers and Selected Efficacy Variables

Correlations will be evaluated graphically using scatter plots, and heat maps displaying such potential associations.

The following correlation coefficients will be calculated by study intervention arm for the different correlation scenarios:

- Pearson's correlation coefficient for two continuous variables.
- Phi correlation coefficient for two binary variables.
- Point biserial correlation coefficient for one binary variable and one continuous variable.

5.5.2.5. Sustained HBsAg Response

Summary tables with counts and percentages of participants who meet each of the definition will be presented if there is at least 1 participant who meet the criteria.

Spaghetti plots for both absolute values and changes from baseline of HBsAg will be presented over time for each of the definition.

5.6. Safety Analyses

All safety analyses will be performed using the safety analysis set. All assessments will be presented by analysis phase (for treatment period 1, for treatment period 2 and FU phase) and overall. All summaries will be descriptive.

Safety and tolerability will be assessed by evaluating treatment emergent-adverse events (TEAEs), physical examinations, ophthalmic examinations, vital signs measurements, clinical laboratory tests (including hematology, blood biochemistry, blood coagulation, and urinalysis), and ECGs.

Continuous parameters will be summarized using the following statistics: number of observations, mean, standard deviation (SD), standard error (SE), minimum, median and maximum, unless specified otherwise. Frequencies and percentages will be used for summarizing categorical data.

Some analysis will be performed by group, as defined in Section 5.1.10.

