4. STUDY DESIGN

4.1. Overall Design

This ISA describes a Phase 2a study of the combination regimen of JNJ-3989 with NA and PegIFN- α 2a. Prior to Protocol Amendment 3, the study intervention also included JNJ-6379. This ISA is a companion document to the Master Protocol PLATFORMPAHPB2001, which describes the common design elements of the Platform study in participants with CHB. This ISA describes specific and/or additional protocol elements applicable to this open-label, single-arm, multicenter, interventional study to evaluate the efficacy, safety, tolerability, and PK of the combination of JNJ-3989, NAs, and PegIFN- α 2a in approximately 50 patients with CHB.

Note that as of Protocol Amendment 3, JNJ-6379 has been removed as study intervention and the study will continue with JNJ-3989, NA and PegIFN- α 2a only. Participants had to stop JNJ-6379 treatment immediately.

Approximately 50 virologically suppressed CHB-infected participants, 18-65 years (inclusive) of age, will be enrolled in this study. Approximately 40% HBeAg-positive participants will be enrolled.

This open-label study will be conducted in 4 periods:

- Screening Period (4 weeks [if necessary, can be extended to a maximum of 8 weeks decided on a case-by-case basis and in agreement with the sponsor]).
- Treatment Period 1 (12 weeks) consisting of combination treatment with JNJ-3989 + NA.
- Treatment Period 2 (12 weeks) adding PegIFN- α 2a to the combination treatment regimen of Treatment Period 1.
- Follow-up (FU) Period (48 weeks).

The total duration of individual participation will be up to 76 weeks (including 4 weeks of screening).

Enrolled participants will start Treatment Period 1 with the following combination treatment regimen for a duration of 12 weeks:

200 mg JNJ-3989 (subcutaneous injection Q4W) +

NA (tablets QD): tenofovir disoproxil (245 mg), or TAF (25 mg), or ETV (0.5 mg). At Week 12, participants who still meet the eligibility criteria for PegIFN- α 2a (see Section 5.2, Exclusion Criteria) will start Treatment Period 2 for a duration of 12 weeks:

200 mg JNJ-3989 (subcutaneous injection Q4W) +

NA (tablets QD): tenofovir disoproxil (245 mg), or TAF (25 mg), or ETV (0.5 mg) +

180 µg PegIFN-α2a (subcutaneous injection once weekly). Participants no longer meeting the PegIFN-α2a eligibility criteria at Week 12 will continue with the Period 1 treatment until Week 24.

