1.2. Study Design

This is a Phase 2a, open-label, single-arm, multicenter study to assess efficacy, safety, tolerability and pharmacokinetics of treatment with JNJ-3989, JNJ-6379 (as applicable), NA, and PegIFN- α 2a in virologically suppressed patients with chronic hepatitis B virus infection. Prior to Protocol Amendment 3, the study intervention also included JNJ-6379. Note that as of Protocol Amendment 3, JNJ-6379 has been removed as study intervention and the study will continue with JNJ-3989, NA and PegIFN- α 2a only. Participants had to stop JNJ-6379 treatment immediately after the implementation of Urgent Safety Measure (USM) and approval of the protocol amendment 3.

Approximately 50 virologically suppressed CHB-infected participants, 18-65 years (inclusive) of age, will be enrolled in this study. Approximately 40% HBeAg-positive participants will be enrolled.

[figure not shown]
The study will be conducted in 4 periods:

- Screening period (4 weeks [if necessary, can be extended to a maximum of 8 weeks decided on a case-by-case basis and in agreement with the sponsor]).
- Treatment Period 1 (12 weeks) consisting of combination treatment with JNJ-3989 + NA.
- Treatment Period 2 (12 weeks) adding PegIFN- α 2a to the combination treatment regimen of Treatment Period 1.
- Follow-up (FU) Period (48 weeks).

The total duration of individual participation will be up to 76 weeks (including 4 weeks of screening).

A schematic of the trial prior to Protocol Amendment 3 is presented in [Figure 1](#).

Figure 1: Schematic Overview of the Study – Prior to Protocol Amendment 3

[figure not shown]

ALT: alanine aminotransferase; DNA: deoxyribonucleic acid; EOS: end of study; EOSI: end of study intervention; FU: follow-up; HBeAg: hepatitis B e antigen; HBsAg: hepatitis B surface antigen; HBV: hepatitis B virus; JNJ-3989: JNJ-73763989; JNJ-6379: JNJ-56136379; LLOQ: lower limit of quantification; n: number of participants; NA: nucleos(t)ide analog; PegIFN-α2a: pegylated interferon alpha-2a; ULN: upper limit of normal; Q4W: every 4 weeks; QD: once daily; QW: once weekly.

^a. If NA treatment completion criteria (HBsAg <10 IU/mL, and HBeAg-negative, and HBV DNA <LLOQ, and ALT <3x ULN) have been met at Week 24, NA will be stopped at the next scheduled visit (ie, FU Week 2), otherwise NA treatment will continue during the complete FU period.

A schematic of the trial as of Protocol Amendment 3 is presented in [Figure 2](#).

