4. POPULATIONS (ANALYSIS SETS) FOR ANALYSIS

Due to a potential impact of future Coronavirus Disease (COVID-19) pandemics on the study data collection, study treatment adherence and study conduct, the modified Full Analysis Set (mFAS) and modified IFN-FAS (mIFN-FAS) are defined to target the estimation of effects without the pandemic-related influences.

The primary set for the efficacy analyses will be the FAS set, and for the safety analyses the safety set. The IFN-FAS and modified FAS/IFN-FAS analysis sets will be used if there is a difference of at least 2 participants between analysis sets.

Table 2: Analysis Sets for Analysis

Analysis Sets	Description
Screened	All participants who signed the ICF for the Master Protocol and an ICF specific for the ISA.
Enrolled	All participants who were enrolled in this ISA.
Full Analysis Set (FAS)	All participants who were enrolled and who received at least 1 dose of study intervention within this ISA.
Modified FAS	All participants who were enrolled and who received at least 1 dose of study intervention excluding those participants who, because of COVID-19 or similar pandemics related reasons, withdrew prematurely from the study prior to Week 24 (end of study intervention [EOSI]), or had no efficacy assessment for the primary endpoint. COVID-19 or similar pandemics related reasons may include for example missed visits due to travel restriction, shortage of lab kits at the planned visit, missed collection of blood sample at key time points for the primary efficacy endpoint, etc.
IFN-FAS	All participants who were enrolled and who received at least 1 dose of PegIFN- α 2a within this ISA.
Modified IFN-FAS	All participants who were enrolled and who received at least 1 dose of PegIFN- α 2a excluding those participants who, because of COVID-19 or similar pandemics related reasons, withdrew prematurely from the study prior to Week 24 (EOSI), or had no efficacy assessment for the primary endpoint. COVID-19 or similar pandemics related reasons may include for example missed visits due to travel restriction, shortage of lab kits at the planned visit, missed collection of blood sample at key time points for the primary efficacy endpoint, etc.
Safety	All participants who received at least 1 dose of study intervention. Participants will be analyzed according to the study intervention they actually received.

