5.1.1. Analysis Phase

The analysis phases are defined in [Table 3](#) below.

Table 3: Analysis Phases Start and End Dates

Analysis Phase	Start date	End date
Screening	The date of signing the informed consent	1 day before the first study agent intake (excluding PegIFN- α 2a)
Treatment Period 1	Date of first study agent intake (excluding PegIFN- α 2a)	For participants who receive PegIFN-α2a: Min [Date of first PegIFN- α 2a intake - 1 day, cut-off date ^b]
		For participants who do not receive PegIFN-α2a: Date of Week 12 study agent intake - 1 day
		For participants who discontinue treatment before Week 12: Max [last intake date of any study agent, study agent discontinuation date, early study withdrawal visit date] + 5 days ^a or cut-off date ^b , whichever occurs first
Treatment Period 2	For participants who receive PegIFN-α2a: Date of first PegIFN- α 2a intake	For participants who did not withdraw from the study prior to the projected/actual Week 24 visit date: Max [last intake date of any study agent, study agent discontinuation date, projected/actual Week 24 visit date] + 5 days ^a or cut-off date ^b , whichever occurs first
	For participants who do not receive PegIFN-α2a: Date of Week 12 study agent intake	
	Otherwise: missing	
Follow-up	Participants who did not withdraw informed consent during treatment period 1 or 2: Max [End date of Treatment Period 1, End date of the Treatment Period 2] + 1 day	Max [study discontinuation date, study completion date] or cut-off date ^b , whichever occurs first
	Otherwise: missing	Otherwise: missing

^a Addition of 5 days is only applicable for Adverse Events and Concomitant Medications.

^b Cutoff dates will be defined to match the prespecified timepoints for DRC safety monitoring, interim analyses, the primary and final analyses, respectively.

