5.1.2.2. Treatment Period 2 Relative Day

The treatment period 2 start date (TP2 Day 1) is defined as the date of first PegIFN- α 2a injection for those who receive PegIFN- α 2a in treatment period 2, and the date of Week 12 agent intake for those who don't receive PegIFN- α 2a. Efficacy and safety assessments during the TP2 will be assigned an analysis study day relative to this date, unless otherwise specified.

The study day in the TP2 phase (TP2 ADY) is defined as:

$$TP2\ ADY = \text{visit date} - TP2\ \text{start date} + 1$$

for visits on or after TP2 Day 1.

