5.1.10. Main Groups for Analysis

While most analyses will be focused on all subjects without separating by study intervention, some analysis will be performed in three different groups:

1. Group 1: Participants who received at least one tablet of JNJ-6379 during treatment period 2:
 - Treatment Period 1: JNJ-3989 + JNJ-6379 + NA
 - Treatment Period 2: JNJ-3989 + JNJ-6379 + NA + PegIFN- α 2a
2. Group 2: Participants who did not receive JNJ-6379 at treatment period 2:
 - Treatment Period 1:
 - JNJ-3989 + JNJ-6379 + NA
 - JNJ-3989 + NA
 - Treatment Period 2: JNJ-3989 + NA + PegIFN- α 2a

Some analysis will be performed separately by the study intervention of treatment period 1 and overall.

3. Group 3: all participants who were enrolled in the trial

Post-hoc analyses may be performed based on duration of exposure to JNJ-6379.

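### Treatment Period 2 safety tables mix participants who did and did not receive PegIFN-α2a, so their rates are not rates in PegIFN-exposed participants

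*SAP*

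**What the plan says.** **Population and layout.** SAP 5.6 fixes one population for safety ("All safety analyses will be performed using the safety analysis set") and one layout: "All assessments will be presented by analysis phase (for treatment period 1, for treatment period 2 and FU phase) and overall". Table 2 in SAP Section 4 defines that population as "All participants who received at least 1 dose of study intervention. Participants will be analyzed according to the study intervention they actually received". A single dose of any component is enough; PegIFN-α2a is not required.

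**Non-recipients are foreseen.** Under Protocol 4.1, participants who no longer meet the PegIFN-α2a "eligibility criteria at Week 12 will continue with the Period 1 treatment until Week 24".

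**They are given a Period 2.** In SAP 5.1.2.2, Period 2 starts at the first PegIFN injection for recipients, "and the date of Week 12 agent intake for those who don't receive" it. Table 3 in SAP 5.1.1 agrees. A participant with neither date, such as one who stops before Week 12, has a Period 2 start of "Otherwise: missing".

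**Splits.** SAP 5.1.10 says "most analyses will be focused on all subjects without separating by study intervention". Its Groups 1 and 2 are separated by JNJ-6379 use in Period 2, and both list PegIFN in the Period 2 regimen; Group 3 is everyone enrolled. SAP 5.1 names no Period 2 regimen without PegIFN. The safety subgroups in Table 9 are sex, age, race, BMI and type of NA.

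**The PegIFN-exposed set.** SAP Section 4 defines the IFN-FAS (at least one PegIFN dose) and brings it in when analysis sets differ by at least 2 participants. SAP 5.2, 5.3.2, 5.4.2 and 5.5.2 restate that rule, as a firm or an optional repeat, for disposition and for primary, secondary and exploratory endpoints. SAP 5.6 does not.

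**The concern.** Period 2 is the only period with PegIFN. A reader will therefore look in its tables for the harms that Protocol 2.3.2.1 attributes to PegIFN (neuropsychiatric, autoimmune, ophthalmologic, hematological and others) and for the added marrow risk of the combination raised in Protocol 2.3.2.2.3. Participants who took no PegIFN in that period contribute to the denominator, and any events they have enter the numerator.

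They are also not a random subset. They leave the PegIFN path because they have come to meet exclusion criterion A25, which covers marrow suppression, low neutrophils, poorly controlled thyroid function and psychiatric disorders. At stake is whether the percentage in a Period 2 table can be read as a rate under the PegIFN combination, both in the final report and in what the DRC sees.

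**Working it through.** **The plan's own figures.** The documents give no PegIFN toxicity rate, no expected number of non-recipients and no Period 2 denominator. The nearest calculable figures are the 90% Clopper-Pearson intervals in SAP Section 3. Recomputed from beta quantiles with 5% in each tail, all eight intervals and widths match to three decimals; for example, 25/50 gives 0.376 to 0.624, width 0.248. The same method serves below as a yardstick for sampling error, although SAP 5.6 plans descriptive safety summaries only.

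**Who is in the Period 2 table.**
1. A participant ineligible for PegIFN at Week 12 stays on the Period 1 regimen (Protocol 4.1).
2. That participant has a Week 12 agent intake, so Table 3 supplies a Period 2 start date.
3. That participant has had at least one dose of study intervention, so is in the safety set.
4. SAP 5.6 tabulates by phase on that set, so the participant's Period 2 data enter the Period 2 table.
5. The by-group option does not remove them. Someone with no JNJ-6379 in Period 2 fits the heading of Group 2 even though the regimen listed there contains PegIFN.

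**Size.** Let N be the number in the Period 2 table, k the non-recipients among them, r the event rate in recipients and r0 the rate in non-recipients:

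table rate = [r(N − k) + r0·k] / N

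If only PegIFN can cause the event, r0 = 0 and the table rate is r(N − k)/N.

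Inputs: N = 50 (SAP 1.2 plans approximately 50 "virologically suppressed CHB-infected participants, 18-65 years (inclusive) of age, will be enrolled in this study"). Assumed, because the documents give neither: k from 1 to 10, and r = 40%.

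| k of 50 | (N−k)/N | r0 = 0 | r0 = 20% | r0 = 40% | r0 = 50% |
|---|---|---|---|---|---|
| 1 | 0.98 | 39.2% | 39.6% | 40.0% | 40.2% |
| 2 | 0.96 | 38.4% | 39.2% | 40.0% | 40.4% |
| 5 | 0.90 | 36.0% | 38.0% | 40.0% | 41.0% |
| 10 | 0.80 | 32.0% | 36.0% | 40.0% | 42.0% |

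Worked entry, k = 5 and r0 = 0: 0.40 × 45 = 18 events; 18/50 = 36.0% against 18/45 = 40.0%. With r0 = 50%: (18 + 2.5)/50 = 41.0%. A PegIFN-exposed denominator gives 40% in every cell. At k = 0 the two coincide.

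Yardstick: the 90% interval for 20/50 is 28.3% to 52.6%, about 24 points wide.

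**Early DRC looks.** DR2 and IA1 are planned at N = 20 (SAP 5.8.3.1 and 5.8.3.2, Table 10). There k = 2 gives a factor of 18/20 = 0.90; for example, 7/18 = 39% would appear as 7/20 = 35%.

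**The case against.** Several points on the other side have force.

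- **The rates need not be diluted.** A reader might infer that the Period 2 rates are diluted. That requires at least one non-recipient and a lower event rate in non-recipients, and the documents establish neither. A25 is applied at screening, so Week 12 ineligibility needs a change in status afterwards and k may be small. For laboratory toxicity, selection for cytopenia or other abnormalities could raise r0 above r. This stands: the direction is fixed only for events that PegIFN alone can cause.
- **The denominator is not stated.** A reader might infer that Period 2 tables divide by the whole safety set. The SAP does not say so. Table 3 gives participants who stop before Week 12 no Period 2, and SAP 5.2 counts participants by phase, so a denominator of those who entered Period 2 is at least as natural. This stands.
- **The IFN-FAS rule may reach safety.** A reader might infer that the PegIFN-exposed set is reserved for efficacy and disposition. The Section 4 sentence follows directly after the safety set is named and is not limited to efficacy. This stands in part: 5.6 puts every safety analysis on the safety set, so the passages conflict or are at best ambiguous. A single non-recipient would not trigger the rule in any case.
- **Other outputs help.** SAP 5.6.2 plans adverse events by relationship to each agent, and 5.6.1 plans PegIFN exposure. The former rests on attribution in an open-label study, states no exposed denominator and does not cover laboratory toxicity. The latter does not correct a rate.
- **The safety set is analyzed by treatment received.** That points toward separation, but SAP 5.1 defines no Period 2 category without PegIFN for it to act on.
- **Summary by period follows Protocol 9.4.3**, which also refers to a Master Protocol section not available here. Summarizing all treated participants by period is legitimate; the point is that it does not give a rate in PegIFN recipients.

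**Conclusion.** The point holds as a mixing problem, not as a demonstrated understatement of toxicity. As SAP 5.6 is written, a Period 2 percentage describes everyone treated in that period, including any participants who never had PegIFN, and no planned split recovers the rate in recipients.

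The effect is modest. For PegIFN-only events at an assumed 40% rate, the table falls short by 1.6 points at k = 2 and by 4.0 points at k = 5 of 50, which is small beside the sampling uncertainty. It reaches 8.0 points at k = 10. These sizes rest on assumed values of k and r and on no such events in non-recipients. The case for changing the plan is that the quantity reported is not the one needed to judge the combination, and that the correction is cheap.

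**What to change.** In SAP 5.6:

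1. Define the Period 2 denominator as participants who entered Period 2, that is, those with a non-missing start date in Table 3.
2. Present the Period 2 adverse event, special-interest event and laboratory toxicity tables for participants with at least one PegIFN injection (the existing IFN-FAS definition), with non-recipients in a separate column or listing.
3. Reconcile Section 4 with 5.6 by stating whether the rule on a difference of at least 2 participants applies to safety. The split in item 2 should not depend on it.
4. Use the same split in the DRC outputs in Table 10 that cover Period 2.

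The cost is SAP wording and a column split, using data already collected and a population already defined. The drawback is an extra column that may hold very few participants and give uninformative percentages; a listing avoids that. This changes analysis only and leaves every dosing, eligibility and stopping rule as it is.
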